13.3.5 Joint Analysis of ABR and Exogenous FVIII/Emicizumab Use

Per the study protocol, subjects will discontinue their regular prophylactic FVIII treatment regimen starting Week 5 post the day of BMN 270 infusion and switch to an episodic treatment schedule. In addition, subjects who experience recurrent bleeding episodes may resume their prior FVIII prophylaxis or start prophylactic emicizumab treatment. Because ABR and exogenous FVIII/emicizumab use are not independent, the following analyses will be performed to jointly assess ABR and exogenous FVIII/emicizumab use:

- Paired analysis of ABR and exogenous FVIII/emicizumab use in each of the efficacy evaluation periods defined in Section 13.1. This analysis enables the interpretation of ABR in the context of exogenous FVIII/emicizumab use.
- Summary of ABR in subgroups of subjects determined by the level of exogenous FVIII/emicizumab use:
 - Subjects who did not resume exogenous FVIII/emicizumab prophylaxis
 - Subjects with zero FVIII infusions
 - Subjects with at least one FVIII infusion
 - Subjects who resumed FVIII/emicizumab prophylaxis
 - Subjects who resumed FVIII prophylaxis
 - Subjects who resumed emicizumab prophylaxis

13.3.6 FVIII activity and ABR in immunosuppression-free periods

To investigate potential confounding effects of immunosuppressant use on the treatment effect of BMN 270, FVIII activity and ABR in immunosuppression-free periods will be assessed for study 270-902 rollover subjects. The immunosuppression-free period is defined as the efficacy evaluation period for subjects who never received immunosuppressants (i.e., systemic corticosteroids or alternative immunosuppressants) and the efficacy evaluation period after the immunosuppressant has been discontinued for subjects who did receive immunosuppressants. The efficacy evaluation period starting from the first date of immunosuppressant use through the last date of immunosuppressant use is considered as the immunosuppression period. For subjects who received and then discontinued immunosuppressants, their ABR in the immunosuppression-free period will be compared to their ABR in the immunosuppression period. This comparison will be repeated for subjects whose immunosuppression-free period is at least one year vs. less than one year. The number of subjects who were off immunosuppressants at various timepoints (e.g. 3, 6, 9, 12, 18, 24 months, etc.) and the corresponding ABR will also be summarized.

For comparison purposes, FVIII activity levels over time and ABR in the efficacy evaluation period will be summarized for subjects who never received immunosuppressants and subjects who were still on immunosuppressants at the time of the data cut-off for the analysis.

13.3.7 Impact of cessation of immunosuppressant or select concomitant medication use on FVIII expression

The impact of cessation of immunosuppressant use on FVIII expression will be evaluated in the mITT subjects who have discontinued immunosuppressant therapy before the data cut-off date for the 2-year analysis. To account for time factor, subjects will be divided into

Study 270-301 Statistical Analysis Plan

subgroups based on their timing of immunosuppressant discontinuation (Weeks 14-26, 27-39, 40-52, et al.). Each subject's median FVIII activity level in the 4 weeks immediately after immunosuppressant discontinuation will be compared to that immediately prior. The median change in FVIII activity will be plotted against the median time to immunosuppressant discontinuation in each of the subgroups.

For comparison purposes, similar analyses will be performed to assess the natural decline of FVIII activity while subjects are on or off immunosuppressants. Changes in FVIII activity levels between 4 weeks before and 4 weeks after Week 20, 24, 28, et al. will be plotted separately for subjects who ever or never received immunosuppressant therapy.

The above analyses will be repeated for select concomitant medications (e.g., lamivudine) to assess the impact of such on FVIII expression in the mITT subjects who have discontinued them before the data cut-off date for the 2-year analysis.

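### The reference curves for FVIII decline on or off immunosuppressants are grouped by ever versus never use, so no on-drug reference exists and the ever-user curve contains the stops under study

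*SAP*

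**What the plan says.** Section 13.3.7 studies the effect of stopping immunosuppression in the "mITT subjects who have discontinued immunosuppressant therapy before the data cut-off date for the 2-year analysis". The within-subject contrast is: "Each subject's median FVIII activity level in the 4 weeks immediately after immunosuppressant discontinuation will be compared to that immediately prior". Subjects are grouped by when they stopped (Weeks 14-26, 27-39, 40-52 and onward), and the median change in each subgroup is plotted.

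A reference is then added, meant to "assess the natural decline of FVIII activity while subjects are on or off immunosuppressants". It consists of "Changes in FVIII activity levels between 4 weeks before and 4 weeks after Week 20, 24, 28, et al", and these changes "will be plotted separately for subjects who ever or never received immunosuppressant therapy". The synopsis repeats both statements, so this is not a slip in one place.

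The same design is reused for select concomitant medications such as lamivudine at the end of Section 13.3.7, and for ALT in Section 14.2.

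Section 13.3.6 already defines status by date: "The efficacy evaluation period starting from the first date of immunosuppressant use through the last date of immunosuppressant use is considered as the immunosuppression period". Section 13.3.7 does not use that definition.

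**The concern.** FVIII activity may fall with time after infusion whatever happens to immunosuppression. A before/after change at cessation can be read only against the change expected over the same weeks in subjects whose immunosuppression did not change, above all those who stayed on it. The plan names the right distinction, on versus off, which varies over time within a subject. It then groups by ever versus never use, which is fixed for each subject.

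If stopping lowers FVIII, stops that fall inside ever-user reference windows deepen the curve labelled as natural decline. The excess drop after cessation then looks smaller than it is, which is the reassuring direction. The question matters to the trial: Section 13.3.6 cites possible confounding of the treatment effect by immunosuppressant use, and the note to file adds analyses in subjects off immunosuppression for at least 12 months.

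**Working it through.** The plan gives no figure for this analysis, so there is none to reproduce. The check has two parts.

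**1. What each curve contains**

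- Every subject in the cessation analysis has taken immunosuppressants, so all of them are ever-users.
- The stop-timing subgroups (Weeks 14-26, 27-39, 40-52 and onward) cover the same weeks as the landmarks (Week 20 onward, every 4 weeks).
- No rule sorts a window by status within it, and none removes a window that contains a start or stop.
- Windows span 8 weeks and are spaced 4 weeks apart. With landmarks assumed to run to Week 100, each stop between Weeks 20 and 96 lies in exactly two ever-user windows, and the nearest landmark is at most 2 weeks away. For a stop at Week 24, the Week 24 reference change is that subject's cessation contrast.
- The never-user curve contains no starts or stops, by definition.
- Neither curve isolates decline while on treatment.

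**2. How much of the effect the ever-user curve absorbs**

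Assumptions, none from the SAP: all ever-users stop; stop times are uniform over L weeks; stopping causes an immediate step D; 4-week means are compared; starts are ignored; the landmark window lies wholly inside the L weeks.

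A stop u weeks from the landmark, with |u| < 4, shifts the after-minus-before contrast by D × (4 − |u|)/4. Over the 8-week window this averages D/2. Hence:

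- share of stoppers with their stop in the window = 8/L
- share of the effect absorbed = (8/L) × 1/2 = 4/L

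For illustration, take a natural change of −2.0 per contrast and D = −5, so the cessation contrast is −7.0. The ever-user curve reads −2.0 − 5 × (4/L).

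| Stops spread over | L (weeks) | Stoppers in window, 8/L | Effect absorbed, 4/L | Ever-user curve | Apparent excess (true −5.0) |
|---|---|---|---|---|---|
| One subgroup, Weeks 27-39 (landmark Week 32) | 13 | 62% | 31% | −3.5 | −3.5 |
| Weeks 14-52 | 39 | 21% | 10% | −2.5 | −4.5 |
| Weeks 14-104 | 91 | 9% | 4% | −2.2 | −4.8 |

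If only a fraction p of ever-users stop in the range, the absorbed share becomes p × 4/L.

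**The case against.** The strongest case against is that this is a wording mismatch in a descriptive plot. Section 13.3.7 has no test, threshold or formal contrast between the cessation plot and the reference plot, and no primary or ranked endpoint depends on it. That stands, and it limits the weight of the point.

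A reader might infer that the whole reference is contaminated and that a cessation effect cannot be separated from natural decline. The SAP does not support this. Two curves are specified, and the never-user curve is clean. The ever-user curve is biased toward no excess effect, by an amount that may be small.

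A reader might also take the 21% of stoppers inside a window as the share of the effect lost. It is not: a stop away from the landmark moves the contrast only in part, and the absorbed share is about half of that. Group medians, which the plan plots for the cessation subgroups, may move less still when only a minority of subjects is affected.

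Nor can never-users be dismissed on the ground that immunosuppression was given largely for ALT elevation. The note to file names ALT elevation as one indication and gives no proportions. Never-users may be a selected group, but the limitation evident from the text is that they cannot show decline on treatment. Distortion from starts is possible but unquantified: no start dates are given, and starts before Week 16 precede every window.

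Related evidence is planned elsewhere: Section 13.3.6 summarises FVIII over time in never-users and in those still on treatment at cut-off (rollover subjects only), and Section 14.2 presents subject profiles. None of it gives a reference change at matched weeks.

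Finally, a wholly-on group is itself selected, since subjects kept on treatment may differ from those who stop at the same week. That is a fair caution for interpretation. It is met by keeping the never-user curve and showing transition windows separately.

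**Conclusion.** The point holds in a limited form. The stated aim (on or off) and the grouping (ever or never) disagree in both the synopsis and Section 13.3.7. As a result no on-drug reference is produced, and the ever-user reference includes the stops it is meant to help interpret.

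The bias runs toward a smaller apparent cessation effect. Its size depends on stop dates that the SAP does not give. Under the assumptions listed, about 10% of the effect is absorbed for stops over Weeks 14-52, about 4% over Weeks 14-104, and about 31% if all stops fall within one 13-week subgroup. Ever-users who never stop would lower these figures; stops clustered at a landmark would raise them. The efficacy conclusions from the ranked tests are unaffected. The correction is worth making because the reference does not answer the question set for it.

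**What to change.** At each landmark, classify each subject's 8-week window from dated immunosuppressant use, building on the period definition in Section 13.3.6:

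- wholly on;
- wholly off after earlier use;
- never used;
- containing a start or stop.

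Exclude the last class from the reference or plot it separately. Keep the never-user curve. Compare each cessation-timing subgroup with the wholly-on curve at landmarks in the same weeks, and state that subjects kept on treatment may differ from those who stop. Because the Section 13.3.6 definition runs from first to last use, say whether gaps between courses count as on or off. Apply the same rule to the select concomitant medications and to ALT in Section 14.2.

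The cost is a change of wording and one derived status flag. It needs no new data, since Section 13.3.6 already relies on first and last dates of use. The downside is fewer subjects per landmark. The note to file records that the 2-year analysis was run in January 2022, so for that analysis the change would mean re-running descriptive output.

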13.3.8 Time to first treated bleed and restart of prophylactic treatment

Time to first treated bleed will be calculated for baseline and Post FVIII Prophylaxis periods for study 270-902 rollover subjects using the following formula:

- Baseline period: Date of first treated bleed in baseline period – Day 1 visit date in 270-902 +1
- Post FVIII Prophylaxis period: Date of first treated bleed Post FVIII prophylaxis – (BMN 270 infusion date +32 or 3 days after the end of FVIII prophylaxis, whichever is later) +1

Subjects who have zero treated bleeds in the baseline and Post FVIII Prophylaxis periods will be censored at the BMN 270 infusion date and the last visit date by data cut-off, respectively.

Time to first treated bleed will be summarized with Kaplan-Meier (KM) curves and KM quartiles (when estimable) for baseline and Post FVIII Prophylaxis periods. 2-sided 95% confidence intervals will be provided for KM quartiles (Klein and Moeschberger, 1997).

Time to first spontaneous treated bleed will be calculated and summarized in the same way as for time to first treated bleed.

Time to restart of prophylactic treatment will be calculated for the Post FVIII Prophylaxis period for all subjects:

- Date of restart of prophylactic treatment – (BMN 270 infusion date +32) +1

The definition of restart of prophylactic treatment is provided in Section 13.1. Subjects who remain on episodic treatment post-BMN 270 will be censored at the last visit date. Kaplan-

Study 270-301 Statistical Analysis Plan

Meier (KM) curves, KM quartiles (when estimable) and associated 2-sided 95% confidence intervals will be provided for time to restart of prophylactic treatment.

Time to restart of prophylactic treatment or the first of ≥ 2 spontaneous treated bleeds ≤ 26 weeks apart (where the first spontaneous treated bleed occurred after two consecutive FVIII activity levels < 5 IU/dL, based on chromogenic assay) will be calculated for the Post FVIII Prophylaxis period for all subjects. It will be calculated as the time from Week 5 (Study Day 33) or 3 days after the end of FVIII prophylaxis, whichever is later, to the restart of prophylactic treatment or the first of ≥ 2 spontaneous treated bleeds ≤ 26 weeks apart (where the first spontaneous treated bleed occurred after two consecutive FVIII activity levels < 5 IU/dL, based on chromogenic assay), whichever is earlier. It will be summarized in the same way as time to restart of prophylactic treatment.

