5.3 Study Day Derivation

Study day is assigned as follows:

- The study drug infusion date is designated as Day 1.
- For visit days after infusion, study day = visit date – Day 1 date + 1.
- For visit days prior to infusion, study day = visit date – Day 1 date (Thus, study days for screening visits are negative numbers.)

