- Efficacy endpoints such as ABR, number of treated bleeds, annualized FVIII utilization, annualized FVIII infusions: will be some of the efficacy evaluation periods listed in [Table 13.1.1](#). In addition, descriptive summary will be provided in Weeks 1-4 and Week 1-end of FVIII prophylaxis (defined as end of week 4 post-BMN 270 infusion or 2 days after end of FVIII prophylaxis, whichever is later).

Time to discontinuation of FVIII prophylaxis post-BMN 270 infusion and duration of efficacy evaluation period for primary analysis of primary and secondary efficacy endpoints will be summarized.

[figure not shown]

Table 13.1.1: Efficacy Evaluation Periods for Analyses of Primary and Second-Ranked Secondary Efficacy Endpoints

Efficacy Evaluation Period	Start Point	End Point	Analysis
Post-FVIII prophylaxis period	Start of Week 5 post-BMN 270 infusion or 3 days after end of FVIII prophylaxis, whichever is later	Last visit by data cut-off	Primary, t-test
Post-FVIII prophylaxis – week 104	Start of Week 5 post-BMN 270 infusion or 3 days after end of FVIII prophylaxis, whichever is later	Last visit by data cut-off or end of Week 104 post-BMN 270 infusion, whichever is earlier	Supportive, t-test
Post-FVIII prophylaxis – restart of prophylactic treatment up to Week 104	Start of Week 5 post-BMN 270 infusion or 3 days after end of FVIII prophylaxis, whichever is later	Last visit by data cut-off, end of Week 104 post-BMN 270 infusion or 1 day before restart of prophylactic treatment, whichever is earlier	Supportive, t-test
Post-FVIII prophylaxis – restart of prophylactic treatment up to last visit	Start of Week 5 post-BMN 270 infusion or 3 days after end of FVIII prophylaxis, whichever is later	Last visit by data cut-off or 1 day before restart of prophylactic treatment, whichever is earlier	Supportive, t-test

Note: end of FVIII prophylaxis is defined as last usual FVIII prophylaxis not followed by another usual FVIII prophylaxis for at least 28 days.

Restart of prophylactic treatment means restart of FVIII or start emicizumab prophylaxis. Restart of FVIII prophylaxis is defined as the first usual FVIII prophylaxis administered at least once a week for ≥ 4 consecutive weeks. Start of emicizumab prophylaxis is defined as the first emicizumab injection among 2 or more emicizumab injections administered within 31 days.

Study 270-301 Statistical Analysis Plan

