	Post FVIII Prophylaxis - 52		Days [the later date of Day 33 or 3 days after the end of FVIII prophylaxis, 368]
	Post FVIII Prophylaxis and Beyond		≥ the later date of Day 33 or 3 days after the end of FVIII prophylaxis
Note: all assessments within the above defined windows will be used to derive the corresponding endpoint.			
Number of FVIII infusions, Bleeds	Baseline ^d		< Day 1
	Week 1 – FVIII Prophylaxis End		Days [1, the later date of Day 32 or 2 days after the end of FVIII prophylaxis]
	Post FVIII Prophylaxis - 52		Days [the later date of Day 33 or 3 days after the end of FVIII prophylaxis, 368]

	Study 270-301 Statistical Analysis Plan
---	--

Assessment	Derived Visit	Scheduled Visit Day ^a	Window ^b
	Post FVIII Prophylaxis and Beyond		≥ the later date of Day 33 or 3 days after the end of FVIII prophylaxis
Note: all assessments within the above defined windows will be used in analysis.			
PROs	Baseline ^c	Day -7 to Day -1	≤ Day 5
	Week 4	Day 29	Days [6, 57]
	Week 12	Day 85	Days [58, 134]
	Week 26	Day 183	Days [135, 274]
	Week 52	Day 365	Days [275, 448]
	Week 76	Day 533	Days [449, 630]
	Week 104/EY	Day 730	Days [631, 812]
	Week 128	Day 897	Days [813, 994]
	Week 156/EY	Day 1096	Days [995, 1176]
	Week 180	Day 1261	Days [1177, 1358]
	Week 208/EY	Day 1461	Days [1359, 1540]
	Week 232	Day 1625	Days [1541, 1722]
Week 260/EY	Day 1826	Days [1723, 1840]	
PBMC (ELISpot)	Baseline ^c	Day -7 to Day -1	≤ Day 1
	Week 2	Day 15	Days [2, 22]
	Week 4	Day 29	Days [23, 36]
	Week 6	Day 43	Days [37, 40]
	Week 8	Day 57	Days [41, 64]
	Week 10	Day 71	Days [65, 78]
	Week 12	Day 85	Days [79, 92]
	Week 14	Day 99	Days [93, 106]
	Week 16	Day 113	Days [107, 120]
	Week 18	Day 127	Days [121, 134]
	Week 20	Day 141	Days [135, 148]
	Week 22	Day 155	Days [149, 162]
	Week 24	Day 169	Days [163, 176]
	Week 26	Day 183	Days [177, 190]
	Week 28	Day 197	Days [191, 204]
	Week 30	Day 211	Days [205, 218]
	Week 32	Day 225	Days [219, 232]
	Week 34	Day 239	Days [233, 246]
Week 36	Day 253	Days [247, 281]	
Week 44	Day 309	Days [282, 337]	
Week 52	Day 365	Days [338, 393]	

	Study 270-301 Statistical Analysis Plan
---	--

Assessment	Derived Visit	Scheduled Visit Day ^a	Window ^b
	Week 64	Day 449	Days [408, 491]
	Week 76	Day 533	Days [492, 575]
	Week 88	Day 617	Days [576, 659]
	Week 100	Day 701	Days [660, 715]
	Week 104/EY	Day 730	Days [716, 772]
	Week 116	Day 814	Days [773, 856]
	Week 128	Day 898	Days [857, 940]
	Week 140	Day 982	Days [941, 1024]
	Week 152	Day 1066	Days [1025, 1080]

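### Time to restart of prophylaxis is counted from Day 33 for every subject, although its declared period and both companion endpoints start later for subjects who stopped FVIII prophylaxis late

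*SAP*

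**What the plan says.** Section 13.3.8 of the SAP introduces the endpoint with "Time to restart of prophylactic treatment will be calculated for the Post FVIII Prophylaxis period for all subjects" and then gives the formula "Date of restart of prophylactic treatment – (BMN 270 infusion date +32) +1". The formula has no term for the date on which the subject's FVIII prophylaxis ended.

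The other two post-infusion endpoints in the section do have that term. Time to first treated bleed subtracts an origin written as "BMN 270 infusion date +32 or 3 days after the end of FVIII prophylaxis, whichever is later) +1". The composite of restart or recurrent spontaneous treated bleeds is "the time from Week 5 (Study Day 33) or 3 days after the end of FVIII prophylaxis, whichever is later" to the first qualifying event.

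The period itself is defined with the same later-of rule. Appendix 20.1 gives its window as "≥ the later date of Day 33 or 3 days after the end of FVIII prophylaxis", and Table 13.1.1 uses the equivalent start point for every efficacy evaluation period. The note to that table defines the end of FVIII prophylaxis as the "last usual FVIII prophylaxis not followed by another usual FVIII prophylaxis for at least 28 days". The synopsis names the period for this endpoint but gives no formula, so it does not settle the matter.

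**The concern.** The label and the formula describe different clocks. A subject who stays on the original prophylaxis past Day 30 enters the Post FVIII Prophylaxis period after Day 33, yet is counted as at risk of restarting from Day 33. While still on original prophylaxis the subject cannot be recorded as restarting FVIII, so that interval is event-free by construction.

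Two things follow:

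- The Kaplan-Meier curve for remaining off prophylaxis credits late stoppers with time during which they were still on it.
- Restart is also a component of the composite. When restart is the first composite event, the same calendar date gives one time in the restart analysis and a shorter one in the composite. Part of any gap between the two curves would then come from the origin and not from recurrent bleeding.

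**Working it through.** The plan attaches no sample size, power or expected event count to this endpoint, so there is no planned figure to reproduce. The check is date arithmetic.

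**Inputs**

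- Study day convention, section 5.3: "The study drug infusion date is designated as Day 1". Infusion date + 32 is therefore Study Day 33.
- E is the study day of the last usual prophylaxis dose. The plan will summarize time to discontinuation of prophylaxis (section 13.1) but gives no distribution, so every value of E below is an assumption.
- Origin as written: Day 33.
- Origin of the declared period and of the companion endpoints: max(33, E + 3).

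**Extra time counted**

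max(33, E + 3) − 33 = max(0, E − 30) days. The two origins agree when E is 30 or less. For E = 85: 85 + 3 − 33 = 55 days.

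**Same restart date, two times.** For a restart on Day 400, the formula as written gives 400 − 33 + 1 = 368 days whatever E is. The later-of origin gives 400 − max(33, E + 3) + 1.

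| E (assumed) | Later-of origin | Extra days | Time as written | Time from later-of origin |
|---|---|---|---|---|
| 30 | Day 33 | 0 | 368 | 368 |
| 60 | Day 63 | 30 | 368 | 338 |
| 90 | Day 93 | 60 | 368 | 308 |
| 120 | Day 123 | 90 | 368 | 278 |

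**Why the extra days hold no FVIII restart.** The 28-day rule puts the earliest FVIII restart at Day E + 28. From the later-of origin, with E of 30 or more, the earliest recordable time is (E + 28) − (E + 3) + 1 = 26 days. As written it is (E + 28) − 33 + 1 = E − 4, that is 56, 86 and 116 days for E = 60, 90 and 120.

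**Effect on the planned output.** The plan reports Kaplan-Meier curves and quartiles, so restart probability is the relevant scale. Assume a constant restart rate of 0.10 per year from the later-of origin, and a share s of subjects whose origin is d days after Day 33. The 1-year restart probability then falls by s × [F(365) − F(365 − d)], where F(t) = 1 − exp(−0.10 t / 365).

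- F(365) = 9.52%, F(335) = 8.77%, F(275) = 7.26%.
- s = 10%, d = 30: 0.10 × 0.75 = 0.07 percentage points.
- s = 10%, d = 90: 0.10 × 2.26 = 0.23 points.
- s = 30%, d = 30: 0.30 × 0.75 = 0.22 points.
- s = 30%, d = 90: 0.30 × 2.26 = 0.68 points.

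The range is about 0.1 to 0.7 percentage points on a 1-year probability of about 9.5%.

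**The case against.** The best defence is that a fixed Day 33 origin is a coherent measure in its own right: time since gene transfer, the same for everyone, in a study with no comparison group. That is fair. It means the defect lies in the mismatch between formula, label and companion endpoints, and not in Day 33 as such. The SAP gives no such rationale, however, and it keeps the period label.

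The practical effect is also limited. Origins coincide for every subject whose last usual dose was by Day 30, discontinuation times are summarized, and section 11 lists separately those who resume prophylaxis, so part of the offset will be visible. The synopsis would replace the curve with a listing if few subjects restart (it suggests fewer than 5), although the listed times would carry the same offset.

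Three stronger readings are tempting but not supported:

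- **That the study's main evidence of durability is compromised.** The SAP does not give this endpoint that role. Section 13.3.2 examines long-term trend through FVIII activity, and the synopsis places time to restart among the additional analyses.
- **That all the added time is immortal.** Restart includes starting emicizumab, which Table 13.1.1 defines without requiring that FVIII prophylaxis has ended. The event-free guarantee holds only for FVIII restart.
- **That the distortion sits entirely early in the curve, or is best stated as a shift in mean time.** Each late stopper's whole record moves, as the Day 400 example shows, and mean time is not a planned output.

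Moving the origin is also not a complete repair. About 26 days without a possible FVIII restart remain because of the 28-day rule. An emicizumab start before the later-of origin would give a zero or negative time.

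**Conclusion.** The inconsistency is real, and nothing elsewhere in the SAP resolves it. Followed as written, the formula adds E − 30 days to the event or censoring time of every subject whose last usual dose falls after Day 30. This tends to raise the curve for remaining off prophylaxis and puts the restart and composite endpoints on different clocks.

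The likely size is small, under 1 percentage point at 1 year. That figure rests on an assumed share of late stoppers, delay and restart rate, none of which the document supplies.

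A reader might infer that the efficacy conclusion is affected. It is not: the endpoint is a descriptive summary outside the nine-step hierarchy in section 13.7, so the primary analysis and the alpha allocation are untouched. This is a correction that should be made, not one on which the trial's result turns.

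**What to change.** Replace the formula in section 13.3.8 with: date of restart − (the later of BMN 270 infusion date + 32 or 3 days after the end of FVIII prophylaxis) + 1. Use the same origin for censored subjects, and keep it identical to the composite's origin. It is safest to define it as the start of the subject's Post FVIII Prophylaxis period, because the Note to File changes the 3-day washout to 3 or 5 days by product type and the origin would then follow. State how an emicizumab start before that origin is counted.

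If Day 33 is intended, say why, remove the Post FVIII Prophylaxis label from this endpoint, and use Day 33 for the composite as well.

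The cost is one formula, one derivation line and one sentence on emicizumab. The dates are already derived for the companion endpoints, so no new data are needed. The Note to File reports that the 2-year analysis was run in January 2022, so the existing curve should be re-derived or footnoted and the corrected origin used in the long-term follow-up.
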